7.4.1.6 Monitoring of Subjects with Adverse Events

AEs are recorded and assessed continuously throughout the trial (see Section 7.4.1.3) and are assessed for final outcome at the End of Trial Visit. All AEs ongoing at the End of Trial Visit must be monitored and followed up by the Investigator until stabilization or until the outcome is known, unless the subject is documented as "lost to follow-up". Reasonable attempts to obtain this information must be made and documented. It is also the responsibility of the Investigator to ensure that any necessary additional therapeutic measures and follow-up procedures are performed.

7.4.2 Pregnancy and In Utero Drug Exposure

Only pregnancies considered by the Investigator to be related to trial treatment (for example, resulting from a drug interaction with a contraceptive medication) are considered to be AEs. However, all pregnancies with an estimated conception date during the period defined in Section 7.4.1.3 must be recorded by convention in the AE page/section of the eCRF. The same rule applies to pregnancies in female subjects and to pregnancies in female partners of male subjects. The Investigator must notify the Sponsor/designee in an expedited manner of any pregnancy using the Pregnancy Report Form, which must be transmitted according to the same process as described for SAE reporting in Section 7.4.1.4.

Investigators must actively follow up, document and report on the outcome of all these pregnancies, even if the subjects are withdrawn from the trial.

The Investigator must notify the Sponsor/designee of these outcomes using the Pregnancy Report Form. If an abnormal outcome occurs, the SAE Report Form will be used if the subject sustains an event and the Parent-Child/Fetus Adverse Event Report Form if the child/fetus sustains an event.

Any abnormal outcome must be reported in an expedited manner as described in Section 7.4.1.4, while normal outcomes must be reported within 45 days after delivery.

In the event of a pregnancy in a subject occurring during the course of the trial, the subject must be discontinued from trial medication immediately. The Sponsor/designee must be notified without delay and the subject must be followed as mentioned above.

7.4.3

Clinical Laboratory Assessments

Fasted blood samples and urine samples will be collected for the clinical laboratory tests (hematology, biochemistry, virology, drugs of abuse, hormones, and urinalysis, [Table 4](#)) following the timing noted in the Schedule of Assessments ([Table 1](#), [Table 2](#) and [Table 3](#)). Additional laboratory safety examinations during the trial are at the discretion of the Investigator. All blood and urine samples will be worked up and analyzed in Nuvisan's clinical laboratory. Any abnormalities in any of the laboratory parameters will be judged by a physician individually in relation to the reference ranges from the laboratory.

For all findings with major deviation and/or possible pathological relevance, follow-up examinations will be carried out until the deviation returns to normal or the absence of pathological relevance can be confirmed. If a deviation considered clinically relevant has not returned to a normal or not clinically relevant value when it is checked during the screening laboratory tests, the subject will not be included in the trial.

Laboratory abnormalities considered clinically relevant by the Investigator will be reported as AE. The following parameters will be determined as summarized in [Table 4](#).

The Sponsor should receive a list of laboratory normal ranges before shipment of the IMP. Any change in laboratory normal ranges during the trial should be forwarded to the Sponsor, including laboratory certificates.

For the amount of blood taken in this study see [Appendix II](#).

Table 4 Safety Laboratory Evaluations

Biochemistry	Aspartate aminotransferase Alanine aminotransferase Alkaline phosphatase γ-Glutamyl-transferase Lactate dehydrogenase Creatine phosphokinase ^a Amylase Lipase	Bilirubin (total) ^b Cholesterol Triglycerides Uric acid	Sodium Potassium Creatinine Urea Glucose
Hematology	Hematocrit Hemoglobin Red blood cell count Mean corpuscular volume Mean corpuscular hemoglobin Mean corpuscular hemoglobin concentration	Platelet count White blood cell count	White blood cell differentials and absolute counts: ^c Basophiles Eosinophils Lymphocytes Monocytes Neutrophils
Urinalysis	pH Nitrite Protein Glucose Leukocytes Blood	Ketone bodies Urobilinogen Bilirubin Urine pregnancy test, females only	Microscopic examination ^d
Urine drug screen	Cocaine Amphetamines Methamphetamines Opiates	Barbiturates Benzodiazepines Methadone Cannabinoids	Tricyclic antidepressants Cotinine Ecstasy
Other tests	Hepatitis B surface antigen Hepatitis C antibody HIV1/HIV2 antibodies Follicle stimulating hormone (if applicable) Thyroid stimulating hormone Serum pregnancy test (beta-HCG), females only eGFR ^e Alcohol breath test (at Screening and each Admission)		

HIV = human immunodeficiency virus, HCG = human chorionic gonadotropin

a In case of an increased creatine phosphokinase (CK), myocardium/brain type (CK-MB) will be determined; if the ratio of CK/CK-MB is above 6, troponin will be determined as well.

b In case of an increased Bilirubin (total) the direct Bilirubin will be determined.

c In case of abnormal findings, manual differential blood count can be requested by the Investigator.

d Only if blood, protein, nitrite, or leucocytes are positive on the dipstick.

e Estimated glomerular filtration rate (eGFR) calculated using the Cockcroft-Gault equation

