List of Abbreviations

Abbreviation	Definition of Terms
AE	Adverse event
anti-HCV	Hepatitis C virus antibody
ALT	Alanine aminotransferase
AST	Aspartate aminotransferase
AUC	Area under the plasma concentration-time curve
AUC _{0-t}	Area under the plasma concentration-time curve from time zero (= dosing time) to the last sampling time (t_{last}) at which the concentration is at or above the lower limit of quantification
AUC _{0-∞}	Area under the plasma concentration-time curve from time zero (= dosing time) extrapolated to infinity
AUC _{extra}	The AUC from time t_{last} extrapolated to infinity
AUC _{extra%}	$AUC_{extra} / AUC_{0-∞} \times 100$
beta-HCG	Beta-human chorionic gonadotrophin
Bpm	Beats per minute
CI	Confidence interval
CK MB	Creatinine phosphokinase myocardium/brain type
CL/f	Apparent total body clearance considering the fraction of dose (f) absorbed
C _{max}	Maximum plasma concentration observed
c-Met	Mesenchymal-epithelial transition factor
CRO	Contract research organization
CV	Coefficient of variation
DDI	Drug-drug interaction
ECG	Electrocardiogram

Abbreviation	Definition of Terms
eGFR	Estimated glomerular filtration rate
eCRF	Electronic Case Report Form
EGFR	Epidermal growth factor receptor
EMA	European Medicines Agency
FDA	Food and Drug Administration
FSH	Follicle-stimulating hormone
GeoCV%	Geometric coefficient of variation in percent
GeoMean	Geometric mean
H	Hour(s)
HBsAg	Hepatitis B surface antigen
HCC	Hepatocellular carcinoma
HGF	Hepatocyte growth factor
HIV1/HIV2	Human immunodeficiency virus 1 and 2
IEC	Independent Ethics Committee
IMP	Investigational medicinal product
λ_z	Terminal rate constant
LLOQ	Lower limit of quantification
Min	Minute(s)
MR _{AUC0-∞}	Metabolite AUC _{0-∞} to parent AUC _{0-∞} ratio
MR _{C_{max}}	Metabolite C _{max} to parent C _{max} ratio
NCI-CTCAE	National Cancer Institute - Common Terminology Criteria for Adverse Events (AEs)
NSCLC	Non-small cell lung cancer
PGx	Pharmacogenetics

Abbreviation	Definition of Terms
PK	Pharmacokinetics
QTcF	Corrected QT interval per Fridericia's formula
RP2D	Recommended Phase II dose
SAE	Serious adverse event
SAP	Statistical analysis plan
StD	Standard deviation
$t_{1/2}$	Terminal half-life
TEAE	Treatment emergent adverse event
TF2	Tablet formulation 2
t_{lag}	Time prior to the first measurable (non-zero) concentration
t_{last}	The last sampling time at which the concentration is at or above the lower limit of quantification
t_{max}	Time to reach the maximum plasma concentration

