Demographic data (incl. height, weight, BMI)	X	
Medical history	X	
Physical examination	X	X
Vital signs (supine blood pressure, pulse rate, body temperature)	X	X
12-lead ECG	X	X
Clinical laboratory (hematology, biochemistry, urinalysis)	X	X
Serology (HIV/hepatitis)	X	
Serum pregnancy test	X ^b	X ^b
Drugs of abuse test / Alcohol Breath Test	X	
Adverse events (AEs)	X	X
Prior and concomitant medication	X	X

ECG = electrocardiogram, FSH: Follicle-stimulating hormone, HIV = human immunodeficiency virus

a Written informed consent must be obtained prior to any Screening activities.

b Women of non-childbearing potential must have a negative serum pregnancy test at Screening and at End of Trial Visit.

Females are considered postmenopausal if they have age-related amenorrhea \geq 12 consecutive months and increased FSH $>$ 40 mIU/mL, or if they have undergone irreversible surgical sterilization by hysterectomy or bilateral oophorectomy or bilateral salpingectomy.

Table 2 Schedule of Assessments – Treatment A (Administration of Tepotinib Alone)

Assessment / Activity	Day	Treatment A			
		-1	1	2 – 4	5 - 7
Hospitalization		X ←-----→ X ^a			
Ambulatory visits					X
In-/exclusion criteria (only in Period 1)	X				
Physical examination	X				
Vital signs (blood pressure, pulse rate, body temperature)	X	X ^b	X ^b		
12-lead ECG	X	X ^c	X ^c		
Clinical laboratory (hematology, biochemistry, urinalysis)	X ^d	X ^d	X ^d		
Pregnancy test	X ^e				
Drugs of abuse / Alcohol breath test	X				
Administration of tepotinib		X ^f			
PK blood sampling			X ^g	X ^g	X ^g
PGx blood sampling (optional, and only in Period 1)	X ^h				
Adverse events monitoring	X ←-----→ X ^j				
Concomitant medication	X ←-----→ X ^j				

ECG = electrocardiogram, PK = pharmacokinetics, PGx = pharmacogenetics

- a Hospitalization from the morning of Day -1 until 72 h after administration of tepotinib and completion of respective clinical activities (= Day 4).
- b Vital signs (blood pressure and pulse rate) will be measured after at least 5 min rest at predose (within 60 min prior to dosing) and 2, 4, 8, 12, 24, 48 and 72 h postdose.
- c 12-lead ECGs will be recorded and printed out after at least 5 min rest in supine position at predose (within 60 min prior to dosing) and 2, 4, 8, 12, 24, 48 and 72 h postdose.
- d Laboratory assessments will be performed on Day -1, before tepotinib administration on Day 1 and before discharge on Day 4.

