		Screening	Tepotinib alone	Tepotinib with omeprazole fasted	Tepotinib with omeprazole fed	End of Trial Visit	Total	
Clinical laboratory tests								
Biochemistry (incl. viral serology, TSH and FSH levels, if applicable)	4.7	1	3 ^a	3 ^b	3 ^b	1	11	51.7
Hematology	2.7	1	3 ^a	3 ^b	3 ^b	1	11	29.7
PK	2.0		21 ^c	21 ^d	21 ^d		63	126.0
PGx (optional)	2.0		2 ^e				2	4.0
Total		2	29	27	27	2	87	211.4

Note: The number of blood samples may increase above the scheduled number. Blood samples for clinical laboratory follow-up determinations may become necessary. Technical failure of PK/PGx blood drawing may lead the Investigator to decide immediately to repeat a single blood drawing to have a sample.

Maximal blood volume drawn: Estimate per Subject in this Study

that will not be exceeded in this planned trial as by experience of the Investigating Institution:

250

FSH = follicle stimulating hormone, PK = pharmacokinetics; PGx = pharmacogenetics, TSH = thyroid stimulating hormone.

Clinical laboratory (biochemistry and hematology) blood samples:

- a Tepotinib alone: before drug administration on Day -1, before tepotinib administration on Day 1 and before discharge on Day 4 = 3 samples.
- b Tepotinib with omeprazole: Day -1, before tepotinib administration on Day 5, and before discharge on Day 8 = 3 samples.

PK blood samples for determination of tepotinib and its metabolites:

- c Tepotinib alone: predose, 15, 30, 45, 60, 90 min, and 2, 3, 4, 6, 8, 12, 16, 24, 36, 48, 60, 72, 96, 120 and 144 h postdose = 21 samples.
- d Tepotinib with omeprazole: predose, 15, 30, 45, 60, 90 min, and 2, 3, 4, 6, 8, 12, 16, 24, 36, 48, 60, 72, 96, 120 and 144 h postdose = 21 samples.

PGx blood samples:

- e PGx blood samples of 2 x 2 mL (optional) to be drawn on Day -1, in Period 1 only = 2 samples.

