## **15.3 Clinical Laboratory Evaluation**

All laboratory data will be reported with SI units. Laboratory parameters will be listed by subject and time-point and summarized indicating the treatment at the respective time-point using descriptive statistics for absolute values and change from baseline over time.. Data listings of abnormalities as per the NCI-CTCAE guideline will be provided. Shift tables for laboratory tests will be presented by treatment. Shift tables will be based on NCI-CTCAE grades, where possible, and on normal ranges otherwise. They will be produced for

- End of Trial versus Screening
- Discharge versus Pre-dose (Tepotinib administration) within periods.

Laboratory values that are outside the normal range will also be flagged in the data listings, along with corresponding normal ranges and NCI-CTCAE grade and will additionally be listed separately.

See section 7.4.3 of the clinical study protocol for a table of the safety laboratory evaluations.

Safety laboratory values are separated into:

- Hematology
- Biochemistry
- Urinalysis
- Other tests

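### The automatic troponin trigger in Table 4 points the wrong way: it fires when CK-MB is a small part of a raised CK and not when it is a large part

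*Protocol*

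**What the plan says.** Table 4 in Protocol 7.4.3 lists the safety laboratory tests, with creatine phosphokinase under biochemistry. Its footnote a adds two conditional tests in sequence:

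- First step: "In case of an increased creatine phosphokinase (CK), myocardium/brain type (CK-MB) will be determined".
- Second step: "if the ratio of CK/CK-MB is above 6, troponin will be determined as well".

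The list of abbreviations gives CK-MB as "Creatinine phosphokinase myocardium/brain type". The footnote states no units for either measurement and does not say whether 6 is a plain ratio or a percentage. The second step is automatic in its wording, but it does not forbid troponin in other cases.

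No other part of the protocol restates or explains the ratio or gives another automatic troponin trigger. SAP 15.3 does not correct it and only refers back: "See section 7.4.3 of the clinical study protocol for a table of the safety laboratory evaluations".

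**The concern.** The cascade runs from total CK, to the fraction labelled as myocardial type, to a cardiac marker. The middle step is useful only if a large fraction leads to the last step. With CK-MB in the denominator, the written rule does the reverse: a small fraction orders troponin and a large one does not.

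What is at stake is safety monitoring in healthy volunteers who have no benefit from taking part. If staff or the laboratory order set follow the footnote as written, a raised CK with a high CK-MB share gets no automatic troponin, while one with a low share gets a test that adds little. The PK analyses are not touched.

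**Working it through.** **Inputs**

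- Trigger: CK/CK-MB strictly above 6, applied once CK is raised (Table 4, footnote a).
- CK-MB is the myocardium/brain type (list of abbreviations and footnote a).
- Scheduled biochemistry samples per subject: 1 at Screening, 3 in each of three treatment periods, 1 at End of Trial (Protocol Appendix II).
- Planned subjects: 12 (Protocol 8.1).

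The plan gives a cut-off but no derived figure, so there is nothing to reproduce. The check is what the cut-off implies.

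**Step 1: direction.** For positive values, CK/CK-MB > 6 is the same as CK-MB < CK/6. At a fixed CK, raising CK-MB can only switch the trigger off. This holds in any units.

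**Step 2: where it switches off**, in reported units:

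- CK 200: 200/6 = 33.3
- CK 400: 400/6 = 66.7
- CK 1000: 1000/6 = 166.7

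Troponin is automatic only while CK-MB is below these values.

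**Step 3: as a share of CK.** Assume both are reported in the same units. The switch point is then 1/6 = 16.7%, whatever the CK level. The last column adds a second assumption, that the intended rule was CK-MB above 6% of CK, which equals CK/CK-MB < 1/0.06 = 16.7.

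| CK-MB share of CK | CK/CK-MB | Rule as written | Assumed intent (share > 6%) |
|---|---|---|---|
| 1% | 100 | fires | does not fire |
| 2% | 50 | fires | does not fire |
| 5% | 20 | fires | does not fire |
| 6% | 16.67 | fires | does not fire |
| 10% | 10 | fires | fires |
| 15% | 6.67 | fires | fires |
| 16.7% (1/6) | 6.00 | does not fire | fires |
| 20% | 5 | does not fire | fires |
| 25% | 4 | does not fire | fires |
| 50% | 2 | does not fire | fires |

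**Step 4: where the two rules differ.** They both fire only for shares above 6% and below 16.7%. At 6% or less, only the written rule fires (an extra test). At 16.7% or more, only the assumed intended rule fires (a missed automatic test). The documents do not fix the intended cut-off. With 5% the zone of agreement is 5% to 16.7%; with 10% it is 10% to 16.7%. The missed zone is 16.7% and above in each case.

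**Step 5: samples the footnote covers.** 1 + 3 + 3 + 3 + 1 = 11 per subject, and 11 × 12 = 132 for 12 completers. This counts where the rule applies, not how often it would misfire. Of the 11, the samples at discharge or End of Trial number 3 + 1 = 4, or 4 × 12 = 48. The documents do not say how many would show a raised CK with a high CK-MB share.

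**The case against.** The best reply is that the practical gap is narrow and well covered.

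- On the 6% reading, the written rule agrees with the intended one between 6% and 16.7%, and at lower shares it only adds a test. The adverse zone is 16.7% and above, and that figure needs same-unit reporting.
- In that zone CK-MB has already been measured, so the value is on record. Protocol 7.4.3 then provides: "Any abnormalities in any of the laboratory parameters will be judged by a physician individually in relation to the reference ranges from the laboratory". For major or possibly pathological deviations, "follow-up examinations will be carried out until the deviation returns to normal or the absence of pathological relevance can be confirmed", which is an obligation. The Investigator may also order further tests.
- Each of the 11 scheduled biochemistry time points has a 12-lead ECG on the same day (Tables 1 to 3). The Investigator reviews ECGs in a timely manner (7.4.4.2), and clinically relevant ECG findings are a stopping criterion (5.5.2).
- The count of 132 includes samples taken before any study drug.
- Section 3 names lipase and amylase elevation as the identified risks and reports no clinically significant ECG findings in 79 healthy subjects.
- The laboratory may already do the sensible thing.

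Most of this stands as a limit on harm. It does not make the rule right. The follow-up duty requires the deviation to be resolved but does not name troponin, so at a high CK-MB share that test rests on individual judgement, which an automatic trigger is meant to replace. The ECG cover is also partial: the only scheduled laboratory sample after tepotinib within a period is the one before discharge, which coincides with the last serial ECG at 72 h, and the ambulatory days that follow schedule none. If the laboratory's practice is sensible, it departs from the protocol text, and the text still needs correcting.

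**Conclusion.** The concern holds. Footnote a states the automatic troponin trigger in the wrong direction. The direction follows from algebra and from the protocol's own label for CK-MB; it needs no outside figure and does not depend on units.

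The 16.7% switch point assumes same-unit reporting. The reading of 6 as a percentage is a further assumption that the documents neither state nor exclude.

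The consequence is limited to safety monitoring and softened by the other provisions. The number of affected samples is unknown and may be zero. Whether the order set follows the footnote literally cannot be seen from the documents. The primary and secondary PK endpoints, the planned comparisons and the precision calculation are unaffected. It should be corrected because it is an explicit safety threshold that misdirects as written, and correcting it is cheap.

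**What to change.** Rewrite footnote a so that troponin is determined when CK-MB/CK exceeds a stated cut-off. Give the units of both measurements and say whether the cut-off is a percentage. Simply inverting the ratio and keeping a bare 6 would not work: in the same units CK-MB/CK cannot exceed 1, so the trigger could never fire. Take the cut-off from the clinical laboratory's procedure, have the medical lead confirm it, and check that the laboratory order set matches.

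The cost is one corrected footnote and one check of the order set. No visits or scheduled samples are added, and the SAP needs no change because it refers back to the protocol table.

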7.4.4 Vital Signs, Physical Examinations, and Other Assessments

7.4.4.1 Vital Signs

Blood pressure (systolic blood pressure [mmHg] and diastolic blood pressure [mmHg]) will be measured according to the oscillometric method using an automated device, which also indicates the corresponding pulse rate. Blood pressure and pulse rate will be measured after at least 5 min in a supine position, according to the schedule of assessments (Table 1, Table 2 and Table 3).

Body temperature will be measured auricular.

Further vital sign measurements during the course of the trial are at the discretion of the Investigator.

7.4.4.2 ECG

Twelve-lead ECGs will be recorded as scheduled in the trial schedule of assessments (Table 1, Table 2 and Table 3) using the ECG system (CardioPerfect®, Welch Allyn). The ECGs will be recorded in supine position after at least 5 min rest.

ECGs will be plotted with a paper speed of 50 mm/s and 10 mm/mV amplitude, with 10 seconds recording duration for all leads and at least 3 complexes, but preferably 5 complexes in each lead.

Per time-point, the ECG will be stored electronically, printed and reviewed in a timely manner by the Investigator. The original printout will be stored with the subject's source data. Electronic data may be transferred to a central ECG laboratory for central reading and further analysis; these results would be reported separately.

ECG printouts will be signed and dated electronically by the person evaluating the ECG. The ECG will be interpreted by the Investigator (normal/abnormal). For abnormal ECGs, the clinical significance (yes/no) must be judged by the Investigator and the abnormality is to be specified.

Additional ECGs during the course of the trial are at the discretion of the Investigator.

7.4.4.3 Physical Examination

The physical examination comprises general appearance, skin, head, neck (including thyroid), eyes, ears, nose, throat, abdomen, as well as neurological, peripheral vascular, musculoskeletal, cardiovascular and pulmonary system.

Physical examination will be scheduled according to the study flow chart (see Table 1, Table 2 and Table 3). Further physical examinations during the course of the trial are at the discretion of the Investigator. Any relevant findings are to be recorded on the Medical History form in the eCRF (for findings from the past that occurred prior to ICF signature) or on the AE form in the eCRF (for findings presently occurring; events existing but unresolved prior to drug administration).

7.4.4.4 Alcohol Breath Test

A commercially available breath analyzer (Alcotest 6510, Draeger Safety GmbH) will be used to determine the concentration of alcohol in the subject's breath per study flow chart (see [Table 1](#), [Table 2](#) and [Table 3](#)).

Additional alcohol breath tests during the course of the trial are at the discretion of the Investigator.

